## General study plan

In total 12 subjects (with the aim of 10 subjects completing the study) will be recruited for the present project of which 50% (n=6) will be men and 50% will be women (n=6) between 18 and 40 years of age. Subjects will have a BMI above 18.5 and under 30 kg/m^2, will be nonsmokers and with no disease diagnosis.

### 5-2 SAMPLE SIZE CALCULATION

As untargeted metabolomics is a data driven approach, which consists in detecting thousands of metabolites in biological samples with various analytical and inter-individual variability, it is not relevant to calculate a unique statistical power to determine the number of subjects. Nevertheless, previous studies showed that metabolomics allows identification of food intake biomarkers in controlled intervention studies with 4 to 20 volunteers

### 5-3 SELECTION CRITERIA

#### 5-3-1 Inclusion criteria

- Healthy males and females
- Aged 18 - 40 years
- BMI >18.5 and < 30 kg/m^2
- Willing/able to consume all test foods (tomato, banana, Fresubin drink) and the standardized meals (rice and chicken)

#### 5-3-2 Exclusion criteria

- Smokers
- Diagnosed health condition (chronic or infectious disease)
- Taking nutritional supplements (e.g. vitamins, minerals) several times a week
- Taking medication (oral contraceptive pill is allowed).
- Pregnant, lactating

- Antibiotics treatment within 3 months prior to intervention
- Vegetarians, as standardized meals will contain meat
- Not willing to follow nutritional restrictions, including drinking alcohol during study days
- Not willing/able to give informed consent or to sign informed consent.
- Not affiliated to National Health Insurance
- Being in exclusion on the National Volunteers Data file or refusing to be registered on the National Volunteers Data file
- Currently participating or who having got 4500€ in this year to have participated in another clinical trial.
- Subjects deprived of their liberty by judicial or administrative decision.

#### **5-4 SUBJECT WITHDRAWAL CRITERIA**

Subjects may discontinue their participation in the study at any time.

The clinical Investigator may remove a subject, if, in his opinion, it is in the best interests of the subject.

A subject may be withdrawn from the study for any of the following reasons:

- Withdrawal of consent - any subject may withdraw from the study at any time
- Significant deviation from the protocol
- Lost of follow up
- Death
- Incidental illness
- Occurrence of a serious or considered serious adverse event or significant alteration in clinical and/or laboratory parameters. In these cases, appropriate actions will be taken. The sponsor will be notified immediately.

When the investigator had no news of the participant, he must have made every effort to contact him, to establish the reason for the discontinuation of treatment, and to suggest the participant to come to an end-of-study visit. If all these attempts to contact the participant failed, the investigator could then declare the participant “lost to follow-up”. The investigator should document all these attempts in the corresponding medical file. If a volunteer discontinues the study before the end of recruitment period, a new volunteer will be included with the same treatment. The investigator will record the reason(s) and the exact time of premature withdrawal of the study in the case report form. If more than one reason will be given, the investigator will indicate the main reason. The investigator will notify the sponsor of study withdrawals immediately using the page provided for this purpose in case report form by faxing to the study monitor.

In the case of withdrawal from the study due to a serious or non-serious adverse event, the investigator will make every effort to collect the information relating to the outcome of the event. If necessary, the information will be collected afterwards. This information will be recorded in that part of the case report form which concern adverse events. If the investigator cannot collect the information from a visit, he will collect it from the doctor ensuring the follow-up of the participant.

#### **5-5 EXCLUSION PERIOD AND PARTICIPATION TO THE OTHER CLINICAL TRIAL**

The subject is not allowed to participate in another clinical trial for the duration of this protocol. In addition, the exclusion period defined in this study is 1 month, timeframe during which the subject cannot participate in another clinical research protocol.

#### **5-6 COMPENSATION FOR VOLUNTEERS**

The subjects will receive 350 € of compensation for the entire participation.

In the case of a premature withdrawal, a calculation of the compensation will be made in proportion to protocol completion, as follows: 50€/kinetics.

Withdraw after the baseline visit: 0 €

Very exceptionally, the investigators may exclude an obviously non-compliant subject. In that case, the volunteer will receive no compensation.

## 5-7 SUBJECT RECRUITMENT

Subjects may be recruited in the community through advertisements in local newspapers, CRNH web site, emailing at INRA and CHRU, flyers at public places, and from existing UEN volunteer database registered at the CNIL.

## 6 – DESIGN OF TRIAL TO BE CONDUCTED

### 6-1 STUDY PROCEDURES

All the participants will give freely their written informed consent before their selection in the study. The investigator or co-investigator will collect written consent from each participant before, or at the latest on, the day of the first study visit. Prior to this, the investigator or his delegate will inform each participant of the objectives, benefits, risks and requirements imposed by the study, as well as the nature of the study products.

The participant will receive an information and consent form in clear, simple language. He will be allowed ample time to inquire about details of the study and to decide whether or not to participate in the study.

Subjects will come to the Investigational Site for screening to determine whether they are eligible to participate in the study. Information on demographics, anthropometrics, vital signs, relevant medical history and concomitant medication and nutritional supplements (including vitamins) will be collected. A blood sample will be collected to measure: full blood count, platelets, CRP (C Reactive Protein), glycemia, ionogramme (Na+, K+, Cl), hepatic, lipid and renal profile. A total volume of 10ml will be collected to perform this biological test. All inclusion and exclusion criteria will be checked by the investigator or co-investigator. Subjects will also complete a food frequency questionnaire (Appendix 2).

Selected subjects will be definitively included after validation of their biological test by the investigators. Subjects will be personally informed by the medical doctor in case of non inclusion if their biological test presents anomalies. Results will be delivered to them confidentially. Their medical doctor will be informed with a letter from the investigator. The results of biological tests will be kept in the envelope dedicated to each volunteer for this study and only people involved in the research will have access to documents (Nurses, co-investigators, dieticians, Clinical Research Assistant) in accordance with Good Clinical Practices.

The volunteers recruited for this project will be asked to eat three different foods, banana, tomatoes and a control drink (Fresubin ® 2kcal fiber) in order to identify novel biomarkers for each test food. Subjects will be randomly assigned to each test food at different time points of the study. As shown in the general study plan, there will be three dietary interventions:

- **Intervention 1:** Volunteers will consume the **control beverage Fresubin ® 2kcal fiber (250 mL)**.

- **Intervention 2:** Volunteers will consume **240g of peeled banana plus Fresubin ® 2kcal fiber (150 mL)**.
- **Intervention 3:** Volunteers will consume **300g of raw tomato with sunflower oil (12g) and Fresubin ® 2kcal fiber (150 mL)**.

Fresubin is a beverage composed mainly of milk protein, vegetable oils (rapeseed oil, sunflower oil) carbohydrates, vitamins minerals and trace elements (Detailed composition in Appendix 3). For the purpose of this study volunteers will drink the neutral flavored beverage.

Each intervention period will be separated by a washout period of at least 3 days (maximum 10 days). Volunteers will be asked to maintain their normal physical activity and diet between intervention periods; they will receive an information form containing the description and objectives of the project. Volunteers will be randomly assigned to a different food at each intervention period.

Following the study design shown in the general study diagram, the **run-in phase (Day1 and Day2)** participants will follow a restricted diet (described in Appendix 4) and will avoid the intake of banana or tomato in any form. On **Day 2** volunteers will also avoid the intake of banana and tomato in any form and will exclude phytochemical-rich foods such as tea, coffee, wine and other plant foods to avoid noise in the metabolomic profile (recommendations described in Appendix 5). For dinner in this day, volunteers will prepare a standardized dinner which composition will be given by the investigators (rice and chicken meal, composition in Appendix 6). After dinner subjects will begin the overnight fasting period. All foods consumed on day 2 will be reported in the 24-hour recall questionnaire applied by a nutritionist the day of the dietary intervention.

In the morning of Day 3, subjects will arrive fasted at Investigational Site at around 7.30 am. As stated previously volunteers will be assigned randomly to one of the three interventions, Fresubin ® 2kcal fiber, 240g of banana plus control drink, or 300g of tomato plus control drink. Throughout the intervention, subjects will have free access to water, maximum 250ml of water per hour until 6 hours after intervention (1.5L in total).

A trained phlebotomist will place a catheter on the subject's arm before the intake of the test foods to collect the baseline sample. Then four other samples will be collected postprandially after **1h, 2h, 4h, and 6h**.

A total of **7 urine samples** will be collected. The first void of urine will be collected by the subjects at home upon the morning of Day 3 and the rest of the samples after the intake of the test foods as follows: **0-1h, 1h-2h, 2h-4h, 4h-6h**. The urine samples corresponding to **6h-12h** and **12-24h** interval will be collected by volunteers at home until the morning of **Day 4**. Urine samples will be kept at 4°C between collections; the use of preservatives will not be needed.

After the 6h collection of blood, the peripheral catheter will be removed and subjects will have lunch composed of rice and chicken meal, then subjects will be allowed to go home. Before leaving the Investigation center, participants will be instructed to prepare a standardized dinner based on chicken and rice. Volunteers will not be allowed to eat or drink anything except water and the standardized dinner.

On the morning of **Day 4**, subjects will arrive fasted at the investigation center at around 7.30 am in order to collect the **24h** blood sample and will deliver the **6h-12h** and **12-24h** urine collection. Afterwards participants will receive a breakfast (free composition) on site and be allowed to follow their normal diet until the run in phase of the following intervention period initiates. This procedure will be repeated for each intervention (1,2,3) separated by a minimum 3 day period (=7 days between visits).

*Table 1. Summary of trial procedures*

	Who	Where
Day 1: Run in		
Restricted diet: no banana or tomato intake	Volunteer	At home
Day 2: Run in		
Restricted diet: no intake of tomato, banana, tea, coffee, wine, fruit juices, plant foods. Dinner based on chicken and rice,	Volunteer	At home
After dinner, beginning of fasting period (8-12 hr)	Volunteer	At home
Day 3: Intervention day		
Urine collection 1 (first void of the morning)	Volunteer	At home
Placement of peripheral catheter	Phlebotomist	UEN
Blood sampling 1 at baseline (0h)	Phlebotomist	UEN
Intake of test food (banana, tomato or control drink)	Volunteer	UEN
Blood sampling 2 (1h)	Phlebotomist	UEN
Blood sampling 3 (2h)	Phlebotomist	UEN
Blood sampling 4 (4h)	Phlebotomist	UEN
Blood sampling 5 (6h)	Phlebotomist	UEN
Urine collection 2 (0-1h)	Volunteer	UEN
Urine collection 3 (1-2h)	Volunteer	UEN
Urine collection 4 (2-4h)	Volunteer	UEN
Urine collection 5 (4-6h)	Volunteer	UEN
Urine collection 6 (6-12h)	Volunteer	At home
Urine collection 7 (12-24h)	Volunteer	At home
At T6h, Lunch intake (rice and chicken meal)	Volunteer	UEN
Restricted diet: Dinner based on chicken and rice. No intake of tomato, banana, tea, coffee, wine, fruit juices, plant foods intake	Volunteer	At home
After the standardized dinner, beginning of the fasting period	Volunteer	At home
Day 4: Day after intervention		
Blood sample collection 6 (24h)	Phlebotomist	UEN
Urine Collection (first void of urine)	Volunteer	At home
Breakfast	Volunteer	UEN

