## SUMMARY

Promotor	INRA
Main investigator	[name]
Co-Investigators	[name], [name], [name]
Title	Identification of new biomarkers of banana and tomato intake
Rational	In epidemiological studies, dietary intakes are assessed by questionnaires, an approach with inherent limitations associated with self-reporting : memory bias, difficulty to estimate portion size, insufficient coverage of the dietary diversity... The use of biomarkers of food intake should markedly improve the accuracy of dietary assessment, However, only few validated biomarkers are available. A large European project (FoodBALL) was funded by the JPI HDHL to identify a large range of new biomarkers of intakes, using untargeted metabolomics on urine and plasma samples collected in a series of controlled nutritional intervention studies.
Objective	The BioBanaTom study aims, in the framework of the FoodBALL project, at identifying new biomarkers of intake for banana and tomato, two important foods of the European diet.
Evaluation criteria	Main Criteria: Identification using metabolomics of plasma and urine metabolites specifically associated to banana and tomato intake, for validation as biomarkers. Secondary criteria : Obtention of reference metabolomics profiles which may be related to metabolic impact of an acute intake of tomato or banana.
Methodology	Cross-over randomized, open, controlled
Number of subjects	12
Undesirable effects	No undesirable effect expected beyond those link to blood sampling (small local hematoma, slight local inflammation)
Recruitment modalities	Volunteer file of UEN declared to the CNIL, mailing CHRU and INRA Clermont-Ferrand-Theix, local medias. The selection of the volunteers will be performed during medical inclusion visits.
Main selection criteria	Inclusion criteria Men and women, healthy (normal medical and biological exam), non-smoking, aged 18 to 40, BMI>18,5 and <30 kg/m  , with no aversion for banana or tomato. Exclusion criteria Smokers, diagnosed with infectious or chronic disease, under medication (except contraception pill), having followed an antibiotic treatment in the last 3 months, consuming dietary supplements several times a week, pregnant and lactating women, vegetarian as the protocol implies consumption of standardized meal containing meat.

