Protocol description	Written consent will be obtained after complete information of the subjects about the objectives, and the nature and possible risks of the study (informed consent form in duplicate, one copy given to the volunteer). The protocol will be explained in details, with objectives and constraints, according to the information form, by the scientist in charge. A clinical exam and a check-up of all selection criteria will be performed by the main investigator or another medical doctor.  At the inclusion visit, subjects will have a medical exam including questionnaire

	
regarding past medical history, family background, medical treatments and standard clinical exam (weight, height, blood pressure) and a blood sampling. A food frequency questionnaire will also be completed. The conformity to the selection criteria will be checked during this medical exam. The selected subjects will be definitely included after validation of the selection criteria by the investigator.
 
The volunteers will consume in 3 distinct experimental periods either a control drink (oral nutritional complement Fresubin, 250 mL), or 240g banana (and 150 ml Fresubin), or 300g tomato (with 12 g sunflower oil and 150 mL Fresubin). Every volunteer will consume the 3 test foods, in a randomized order. After test food intake, urine will be collected over 24h in 7 fractions. Blood samplings will be performed before the food consumption (t0) and in post-prandial period (4 samplings at 1h, 2h, 4h et 6h), as well as on the following day in fasting state (t24h). the volunteers will follow a tomato and banana-free diet during the study days, as well as a more restrictive diet, without plant-based food, on the sampling days and on the day before. A 24h recall will be filled for the dietary intakes on the day before the sampling days (D2).
 
Samples will be analyzed using an untargeted metabolomics approach (LC-MS, GC-MS et RMN) with the aim to identify new biomarkers of tomato and banana intake.
 
The total volume of sampled blood will be 154 ml per subject.

Duration	
Duration of the study for every volunteer : 8 weeks
 
Total duration of the study: 6 months for the subject selection and realization of all experimental periods for all the volunteers
 
Total duration of the project : 3 years

Indemnities	350€ per subject

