The diversity of compounds found in food metabolomics represents a major challenge and so in an international effort to improve dietary biomarkers identification and validation, the Food Biomarkers Alliance (FOODBALL) has been created. In this project, 22 institutions from 11 different countries will collaborate in three main tasks: 1) Discovery of new dietary biomarker using a metabolomic approach, 2) systemic validation of existing and newly discovered biomarker to achieve a good coverage of food intake in different European populations and 3) exploring biological effects using biomarkers of intake (<http://foodmetabolome.org/>). With the latter, the necessity of building a chemical library that allows the use of standards for further identification arises. Along with FOODBALL, The Food Compound Exchange (FoodComEx) aims to improve availability of analytical standards of biological compounds to achieve a better and easier biomarker identification (<http://foodcomex.org/>).

As part of INRA collaboration to FOODBALL and FoodComEx, the present project attempts to identify biomarkers of banana and tomato intake, through the exploration of the serum and urine metabolome of subjects who consumed these foods in a controlled intervention. The same study design will be applied in six different centers within Europe to assess biomarkers of the intake of 12 public health related foods.

Tomatoes were introduced to European countries in the 16th century. The origin of tomatoes may be tracked back to the Aztec civilization in Mexico. There are fifteen leading countries in the production of tomato China, US, India, Turkey, Egypt, Italy, Spain, Brazil, Iran, Mexico, Greece, Russian Federation, Ukraine, Chile and Uzbekistan which supports the fact that tomatoes are between the five most eaten vegetables in the world. Tomatoes contain a large variety of micronutrients ( $\beta$ -carotene as pro-vitamin A, vitamin C, folate, and potassium) and other chemical compounds, including lycopene and polyphenols that are considered beneficial for health. Most of the published work on tomato is mainly focused on the association between the intake of lycopene and flavonoids, such as naringenin and hesperetin, and a lower risk for chronic diseases and cancer, however

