**8 – TRIAL TREATMENT, DOSAGE FORM, AND DOSAGE REGIMEN OF THE INVESTIGATIONAL PRODUCTS**

**8-1 INVESTIGATIONAL PRODUCT/TREATMENT**

Bananas and tomatoes will be bought in a local grocery. A unique dose of 240g banana and 300g tomatoes will be given to the volunteers.

The control drink will be **neutral flavored Fresubin® 2kcal fiber**. Volunteers will drink 250 mL on the Intervention 1 (volunteers only drink Fresubin® 2kcal fiber as a control) and 150 ml of Fresubin plus the test food of interest on Intervention 2 (Fresubin® 2kcal fiber plus 240g of banana) and Intervention 3 (Fresubin® 2kcal fiber plus 300g of tomatoes).

Nutritional composition of Fresubin® 2kcal fiber is as follows:

Nutritional Composition		Per 100ml	Per 200ml
Energy	kcal	200	400
Protein	g	10	20
Nitrogen	g	1.6	3.2
Carbohydrate	g	22.5	45
Of which sugars	g	3.2-5.8*	6.4-11.6

Of which lactose	g	≤0.3	≤0.6
Fat	g	7.8	15.6
Of which saturated fatty acids	g	0.6	1.2
Of which polyunsaturated fatty acids	g	1.4	2.8
Of which monounsaturated fatty acids	g	5.8	11.6
Fibre	g	0, 1.5-1.6 	0, 3.2 
Water	ml	69-70*	138-140*
Osmolarity	mosmol/l	495-650	
Osmolality	mosmol/kg H2O	720-950	

*Information obtained from: <http://www.fresenius-kabi.co.uk/4727.htm>*

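### Sunflower oil is added to the tomato meal only, so tomato candidates describe tomato with oil, and no stage of the plan states an origin rule (minor)

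*Protocol*

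**What the plan says.** The Protocol Summary gives the tomato meal as "300g tomato (with 12 g sunflower oil and 150 mL Fresubin", and section 6-1 agrees: "300g of raw tomato with sunflower oil (12g) and Fresubin ® 2kcal fiber (150 mL". The banana meal is "240g of peeled banana plus Fresubin ® 2kcal fiber (150 mL" and the control is 250 mL of Fresubin; neither has added oil. Section 6-1 also gives the make-up of the drink: "Fresubin is a beverage composed mainly of milk protein, vegetable oils (rapeseed oil, sunflower oil) carbohydrates". Appendix 3 names the same two oils. Neither place gives their proportions.

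Three other descriptions of the tomato meal leave the oil out. Section 4 names only the tomato. The Day 3 text of section 6-1 lists "240g of banana plus control drink, or 300g of tomato plus control drink". Section 8-1 has "Intervention 3 (Fresubin® 2kcal fiber plus 300g of tomatoes".

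The main criterion in the Summary is the identification of "metabolites specifically associated to banana and tomato intake, for validation as biomarkers".

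For urine, the SAP fits a three-class PLS-DA and then compares each food with control. A candidate needs VIP above 2, a BH-adjusted p below 0.05 and higher intensity in the food arm. For plasma, each food is again set against control. An ion must exceed its 0 h level at p < 0.01, have VIP above 2 and be higher with the food.

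After selection, section 7-2-3 plans accurate mass, molecular formula and a search of chemical databases. Section 2 lists among the consortium's tasks the "systemic validation of existing and newly discovered biomarker to achieve a good coverage of food intake".

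**The concern.** The main criterion asks for metabolites specific to tomato. The tomato meal differs from both other meals by two plant products, the tomato and the added oil. An ion that comes from the oil and rises after the meal looks, to every planned analysis, like an ion that comes from the tomato.

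Randomised order, the crossover, false-discovery control, cross-validation and permutation testing do not help. They address chance and period effects, not two components that are always given together.

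At stake is the attribution of some tomato candidates. The same ambiguity reaches the reference samples and profiles of section 3-2 and the shared pools of section 7-1-2, which others would use to identify metabolites of tomato components.

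**Working it through.** The documents give no figure for this point, so there is none to reproduce. The check has four steps.

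**1. Can tomato and oil be separated?** Code each meal by its components: Fresubin in units of 100 mL, banana, tomato, added oil.

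- Control: (2.5, 0, 0, 0)
- Banana: (1.5, 1, 0, 0)
- Tomato: (1.5, 0, 1, 1)

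Over (control, banana, tomato) the tomato column is (0, 0, 1) and the added-oil column is (0, 0, 1). They are identical, so the matrix has rank 3 for four components. Tomato versus control estimates tomato plus oil minus 100 mL of Fresubin; the same quantity without the oil is not estimable. Adding subject and period effects for 12 subjects does not change this (six sequences used twice, an assumption, since the documents do not list the sequences). The banana arm does not help, because it has neither component.

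**2. Total fat.** Fresubin has 7.8 g fat per 100 mL (section 8-1 and Appendix 3 agree). The foods' own fat is not given and is left out.

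- Control: 250 × 0.078 = 19.5 g
- Tomato meal, Fresubin part: 150 × 0.078 = 11.7 g
- Tomato meal with oil: 11.7 + 12 = 23.7 g
- Tomato minus control: 23.7 − 19.5 = +4.2 g with oil; 11.7 − 19.5 = −7.8 g without it

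The oil brings the two meals closer in total fat. The point therefore concerns constituents of sunflower oil, not fat in general.

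**3. Sunflower oil.** Let s be the share of Fresubin fat that is sunflower oil. It is not stated. Both oils are listed, so 0 < s < 1. Assume that the added oil and the sunflower oil in Fresubin have similar constituents.

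- Control: 19.5s g
- Tomato meal: 12 + 11.7s g
- Difference: 12 + 11.7s − 19.5s = 12 − 7.8s g
- Ratio: (12 + 11.7s) / 19.5s

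| s (assumed) | Control, g | Tomato meal, g | Difference, g | Ratio |
|---|---|---|---|---|
| 0.25 | 4.875 | 14.925 | 10.05 | 3.06 |
| 0.50 | 9.75 | 17.85 | 8.10 | 1.83 |
| 0.75 | 14.625 | 20.775 | 6.15 | 1.42 |

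The limits, which are not reached, are 12 g as s approaches 0 and 4.2 g (ratio 1.22) as s approaches 1. The difference is positive for every s, so the oil in the control drink never cancels the added oil. The ratio matters as well as the grams, because the SAP's OSC filter uses log-transformed data.

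**4. Does any stage ask about origin?** The urine and plasma rules use size, significance and direction only, and an oil-derived ion can satisfy all three. The steps in section 7-2-3 can say what a compound is, but no criterion says which part of the meal it came from. Validation is named in the Summary and section 2 without such a criterion.

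**The case against.** The strongest reply is that this is a discovery study and its claims are already modest. Section 3 speaks of potential biomarkers, and the SAP speaks of candidates and plausible markers. Validation is a separate task. Identification is also well resourced: accurate-mass LC-MS, GC-MS and NMR on both fluids, and access to a library of standards. An analyst may well recognise a lipid from the oil. All of this stands, and it limits the harm to a false lead. It does not supply a rule, and an ion that stays unidentified cannot be recognised.

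The second reply is that the control drink contains sunflower oil but no tomato. At moderate or high s, an oil ion shows only a modest contrast with control and competes poorly for VIP above 2. This also stands. At low s the ratio is large, and the documents do not say which case applies.

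Stronger readings are tempting but not supported:

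- A reader might take the full 12 g as the excess over control. That needs a Fresubin without sunflower oil, which section 6-1 and Appendix 3 exclude.
- A reader might cite the oil's share of the tomato meal's fat, or the gap to the banana meal. Neither enters a selection rule; candidates are selected against control.
- A reader might object that high-resolution work covers only some urine samples. That step establishes what a compound is and does not need every sample.
- A reader might infer from the differing meal descriptions that the oil was not always given. The Day 3 text refers back to the earlier definition, and the mismatch is editorial.

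**Conclusion.** The point holds as a minor one. The aliasing is exact: it follows from the meal definitions in the Summary and section 6-1 and needs no assumption about variability or sample size. The excess of sunflower oil over control lies strictly between 4.2 and 12 g. Its size within that range, and the ratio, depend on the unstated share s and on the two sunflower oils being alike.

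As designed, the data support statements about tomato eaten with sunflower oil. The documents do not show that any oil-derived ion will be selected, or how many, so it would be wrong to conclude that the tomato results are invalid or that a false marker will be confirmed. Banana versus control is unaffected, since neither meal has added oil.

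**What to change.** 1. Reconcile sections 4, 6-1 (Day 3 text) and 8-1, which omit the oil, with the Summary and the definition of Intervention 3 in section 6-1.
2. If the reconciled meal includes the oil, describe the contrast, and any claim drawn from it, as tomato with sunflower oil versus control. Label the shared reference samples and pools of sections 3-2 and 7-1-2 in the same way.
3. Add to the SAP, at the identification step already planned in section 7-2-3, a check of each tomato candidate in urine and blood against known sunflower-oil constituents and their metabolites. Report matches as not attributable to tomato alone: flagged, not dropped. Unidentified candidates keep the wording in item 2.

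The cost is a few wording edits and one SAP paragraph that uses a database search already planned. No new participants or samples are needed. An LC-MS run of the oil is optional and depends on the product being available, which the documents do not state; it would not show human metabolites of the oil.

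The check has limits. Some true fat-soluble tomato compounds that also occur in the oil may carry the flag, and the absence of a match does not prove tomato origin.
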